Patients with previous diagnosis of histoplasmosis will not be considered for this study. We will also exclude pregnant or lactating woman, patients with renal failure (serum creatinine and urea >1.5 times the upper limit of normality), abnormal aminotransferases (up to >3 times the upper limit of normality), and patients with a previous serious reaction to a polyene antifungal drug. Patients who received more than one dose of a polyene antifungal drug in the last 48 hours will be excluded, as well as patients who refuse content to participate in the study. Patients diagnosed with histoplasmosis affecting the central nervous system will not be allowed to participate in the study. In addition, patients who are expected to die within 48 hours of enrolment will also be excluded, based on the judgment made by the attending physician. Patients diagnosed with tuberculosis will be excluded; as well those receiving drugs that cause significant drug-drug interaction (relative or absolute) with itraconazole.

Study settings

Six medical centers in Brazil, will recruit patients for this study: Santa Casa de Misericórdia de Porto Alegre, Hospital de Clínicas de Porto Alegre, Hospital Nossa Senhora da Conceição, Hospital de Doenças Tropicais, Hospital São Jose de Doenças Infecciosas, and Hospital Giselda Trigueiro.

Intervention

AIDS patients with DH will be randomized to one of three study arms: (i) single IV dose of L-AmB at 10 mg/kg; (ii) single IV dose of 10 mg/kg of L-AmB on day 1, followed by 5 mg/kg of L-AmB on day 3; and (iii) L-AmB at 3 mg/kg IV for 2 weeks. Induction therapy will be followed in all patients by oral therapy with itraconazole capsules at 400 mg/daily for a year.

Drug reconstitution and administration

L-AmB (AmBisome; Gilead Sciences, San Dimas, California, USA), a lyophilized liposomal preparation of amphotericin B, will be reconstituted according to the manufacturer's instruction and given intravenously at fixed doses, according to the randomization arm. L-AmB concentration should be of 0.2 mg/ml in 5% dextrose, and the drug should be infused over 2 hours, preferably in a central line. Patients will be monitored for the occurrence of infusion-related toxicity during and after drug infusion.

Primary endpoint

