Clinical and mycological successes will be the primary outcomes for this study. A successful clinical response to induction therapy will be defined according to, as a maximum daily temperature $<37.8^{\circ}\text{C}$ for 72 hours; no increase in severity of clinical signs, symptoms, or laboratory abnormalities attributable to histoplasmosis; and the resolution of at least one of the signs or symptoms of histoplasmosis that qualified the patient for study enrollment [7].

Primary study outcome will be determined at day 14 of the study.

Secondary endpoints

Overall mortality and investigator-attributable mortality due to histoplasmosis will be determined at day 14 of study. Overall Survival (OS) will also be determined at 12, 24, and 48 weeks of study. OS will be considered as the time from randomization until death from any cause.

Secondary endpoint will also include need for an additional antifungal course with L-AmB, during 24 weeks of follow up.

Median percentage of change in renal and hepatic function at 14 days will be compared with baseline values.

Frequency of infusion-related toxicity with L-AmB will be recorded.

Clearance of blood cultures will not be used as a criterion for mycological response in this study, due to the limited sensitivity of blood culture in histoplasmosis [19]. Fungal clearance will also not be used as a criterion for mycological response. Differently from cryptococcosis, in which fungal burden is easily obtained and quantified in cerebrospinal fluid samples,

in histoplasmosis commonly a single positive sample is obtained along patient investigation (e.g., microscopy, culture, and/or histopathology).

Non-culture laboratory markers have proved to be useful adjuncts in monitoring the response to systemic histoplasmosis [20, 21]. In this study, we will evaluate the effect of a decrease of at least 50% in *Histoplasma* urinary antigen concentrations [19] along the first 2 weeks of therapy as a secondary endpoint, and the association of such reductions with clinical response to antifungal therapy.

Rescue therapy

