The study protocol will allow patients to receive additional courses of L-AmB (at 3 mg/kg daily) in case the attendant physician suspect of absence of response with the induction regimen. This will apply for failing patients receiving a single 10 mg/kg of L-AmB; or 10 mg/kg on day 1, followed by 5 mg/kg on day 3. In these cases, L-AmB should be given up to a maximum period of 2 weeks. The estimated frequency of L-AmB as rescue therapy will be based on the frequency of failure with L-AmB at 3 mg/kg in patients with DH and AIDS (i.e., 12%) [7]. Considering that 66 patients will be evaluated in arms (i) and (ii) of the study (high-doses of L-AmB), in a pessimistic scenario we aim to provide 8 additional treatments with L-AmB.

Time for initiating ART

Physicians will be instructed to initiate ART as soon as possible in AIDS patients with DH, since immune reconstitution syndrome is uncommon in patients with DH [22]. In Brazil, initial ART consists of dolutegravir, lamivudine, and tenofovir. History of previous antifungal use and known resistance patterns will also be considered in the decisions about ART.

Statistical analyses

Descriptive statistics will be used to summarize the data. Mean, standard deviation, median, interquartile range and minimum and maximum will be described for continuous variables. Categorical variables will be summarized by absolute and relative frequencies. Kaplan-Meier method will be used in order to describe OS. Despite the non-comparative status of the

trial, exploratory comparisons will be performed across subgroups. Continuous variables will be compared using two sample t-test, paired sample t-test, Mann-Whitney test, Wilcoxon signed-rank test, one-way ANOVA or Kruskal-Wallis test, as appropriate and necessary. Categorical variables will be compared with Fisher exact test or chi-square test, as appropriate. All p-values will be two-sided.

We expect that the three arms will have the same clinical response. For each arm, when the sample size is 29, a two-sided 90% confidence interval will extend 10% from the observed proportion for an expected proportion of response equal to 88% [as extracted from the Johnson trial]. Considering a dropout of 10%, the sample size per arm will be 33. The total sample size for the study will be 99 patients. Data analysis will be performed using SPSS software.

Ethical aspects

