Conduction of this study is conditioned to ethical approval by local IRBs. Since this trial will not aim to modify any regulatory aspect related to L-AmB in Brazil, ANVISA (Brazilian Health Regulatory Agency) will not be consulted. The study will also be registered at clinicaltrials.gov.

Study activities

Clinical evaluations will take place at baseline, day 3, day 7, and day 14 (End of Study Visit). End of follow up will occur at week 48, and mortality will be determined at weeks 12, 24, and 48.

The study will recommend careful attention to hydration status, and close monitoring of renal function, hepatic function, and electrolytes. Unless clinically advisable, physicians are requested to give one liter of saline 0.9% solution intravenously before L-AmB infusion. Patients should also be on prophylaxis with daily trimethoprim-sulfamethoxazole.

Table 1 shows the procedures predicted for this study. Clinical and laboratory adverse events will be graded using the NIH DAIDS Toxicity Table [23]. Itraconazole therapeutic drug monitoring will be offered to sites at day 7 and day 14 of study. The attending physicians will use this information according to their personal judgment.

Table 1. Study activities.

	Baseline	Day 3	Day 7	Day 14	Week 12	Week 24	Week 48
Informed Consent	X						
History	X						
Physical Exam	X		X	X			
Maximum Temp	X	X	X	X			
Glasgow coma scale	X		X	X			
Chemistry (including magnesium) and blood counts	X		X	X			
HIV documentation	X						
CD4 count determination							
Pregnancy Test	X						
Chest X-ray	X			X			
Study Drug accountability	X						
Concomitant medications	X	X	X	X			
Adverse Events		X	X	X			
Survival determination				X	X	X	X
Molecular test for TB	X						
Urine for Histo antigen test	X		X	X			
Histoplasma PCR (as needed)	X						
Fungal culture (as needed)	X						
Microscopy (as needed)	X						
Histopathology (as needed)	X						
Itraconazole TDM			X	X			
Lysis centrifugation (if available)	X						
Study responde determination				X			
Need for additioal course of L-AmB				X	X		

Study Plan Schedule Strategy

Table 2 shows the predicted timeline for this study.

Table 2. Study plan.

References

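### The exception in the pre-infusion saline instruction is inverted as written and conflicts with the hydration advice beside it; the sponsor must reconcile the two

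*Combined protocol and SAP*

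**What the plan says.** Two consecutive sentences in the Study activities section deal with fluids. The first is general: "The study will recommend careful attention to hydration status, and close monitoring of renal function, hepatic function, and electrolytes". The second is the operative instruction: "Unless clinically advisable, physicians are requested to give one liter of saline 0.9% solution intravenously before L-AmB infusion".

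The Secondary endpoints section makes renal function an outcome: "Median percentage of change in renal and hepatic function at 14 days will be compared with baseline values". Table 1 schedules chemistry at baseline, day 7 and day 14. It has a concomitant-medication row at baseline and days 3, 7 and 14, and no row for pre-infusion fluid. The Study settings section names six centres.

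**The concern.** The second sentence tells a physician what to do at the bedside before giving a drug whose renal effects the trial measures. Its exception points the wrong way relative to the sentence before it. A site that follows the words and a site that follows the apparent sense would treat the same patient differently, and both could claim to be following the protocol. Adherence cannot be monitored against a sentence with no settled meaning.

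Two things are at stake. One is patient safety, because this is a safety instruction. The other is the day-14 renal change. The protocol itself places the saline request next to its advice on hydration and renal monitoring, so it treats them as connected. If hydration practice varies with each site's reading, that variation enters the renal data without being planned or labelled.

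**Working it through.** This is mainly a question of wording, so the check sets the passages side by side.

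**Step 1. Literal reading of the saline sentence.** An instruction of the form *unless A, do B* asks for B when A is false and is silent when A is true.

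| Physician's judgement | What the sentence asks |
|---|---|
| Saline is advisable | The request lapses; saline is neither asked for nor forbidden |
| Saline is not advisable | The request stands |

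Both rows sit badly with the preceding sentence, which asks for care over hydration status.

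**Step 2. Is the rule settled elsewhere?** Drug reconstitution and administration covers the diluent, concentration, infusion time, preferred line and monitoring for infusion reactions. It does not cover fluid before the infusion. Intervention and Rescue therapy give doses and durations only. Table 1 has no entry for it. Nothing restates or clarifies the exception.

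**Step 3. Can a site reconstruct one meaning?** At least two repairs are possible. A negative may have been dropped, so that saline is the default and a reason is needed to omit it. Or *unless* may stand where *if* was meant, so that saline follows only from a positive judgement that it is advisable. The two differ for a patient about whom the physician has no firm view. The text does not choose between them, and this review does not either.

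**Step 4. Effect on the day-14 renal change.** A figure would need the effect of one litre of saline on the renal measure, the spread of that measure, and the share of sites acting on each reading. The documents give none of these, so neither size nor direction can be computed. The wording is the same for all arms, and nothing links a site's reading to an arm. With 33 patients per arm and six centres, the average is 33 / 6 = 5.5 patients per arm per centre if recruitment is equal (an assumption). The documents describe no stratification by centre, so differing site practice could fall unevenly across arms by chance. That supports added variation, not a bias with a known direction.

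**Step 5. Does it reach the sample size?** The Statistical analyses section states that "when the sample size is 29, a two-sided 90% confidence interval will extend 10% from the observed proportion" and gives this "for an expected proportion of response equal to 88" per cent. Reproducing it:

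- n = z² p(1 − p) / d² = 1.645² × 0.88 × 0.12 / 0.10² = 28.57, rounded up to 29
- half-width at n = 29: 1.645 × √(0.88 × 0.12 / 29) = 0.0993, about 10%
- 10% dropout: 29 / 0.9 = 32.2, rounded up to 33
- three arms: 3 × 33 = 99

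All match the plan. Correcting the saline sentence changes none of them.

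**The case against.** The best case against the point is that this is an obvious slip. The preceding sentence shows the general intent, the literal reading makes little clinical sense, and the document has other slips of the same kind. For example, the aminotransferase exclusion combines an upper bound with a greater-than sign. Most sites would probably guess sensibly, and six sites acting in opposite ways is conjecture. The trial is labelled non-comparative, the renal endpoint is secondary and compared with baseline, and Table 1 already has a concomitant-medication record.

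Much of this stands and limits how far the point goes. It does not remove the point: an operative safety instruction should not depend on a guess, and Step 3 shows that a sensible guess is not unique.

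A reader might infer more than the documents support:

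- **That the protocol withholds saline.** It does not. Physicians are asked to give it, and the exception only lifts that request.
- **That the renal endpoint is distorted.** Step 4 shows that no effect can be computed. Possible added variation is as far as the text goes.
- **That saline in a whole arm becomes nil or full depending on the reading.** The exception works patient by patient, so no reading sets an entire arm to either.
- **That the error creates an imbalance of 1, 2 and 14 litres between arms.** Those totals are one litre times 1, 2 and 14 infusions. They assume saline before every infusion, which the sentence does not spell out, and daily dosing in the third arm, for which Intervention says only "iii) L-AmB at 3 mg/kg IV for 2 weeks". They leave out rescue courses in the first two arms, for which the plan provides 8 (0.12 × 66 = 7.92), each lasting up to 2 weeks. Any such difference follows from the regimens and would remain after the wording was corrected, so it is no part of this point.

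**Conclusion.** The point holds as a wording error in an operative safety instruction: the exception is inverted as written and contradicts the adjacent hydration advice. It rests on the text alone and needs no outside figure.

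The consequences are modest and not quantified. Differing site readings could affect patient safety and add variation of unknown size to one secondary endpoint. This assumes that at least some sites read the sentence differently, which is possible but not shown. The planned numbers are unaffected, as is the definition of the primary endpoint. The correction is worth making because it is an instruction that sites act on and it costs almost nothing.

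**What to change.** The sponsor should reconcile the exception with the hydration sentence before it, so that the instruction has one meaning at all six sites, and notify the sites. The clinical content of the rule is the sponsor's decision.

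Optionally, pre-infusion saline can be noted in the existing concomitant-medication record, so that any variation in practice is visible when the day-14 renal change is read.

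The cost is one corrected sentence and a site memo, plus an entry in an existing record if the option is taken. There is no added visit or procedure and no change to the sample size.
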